Non-Interventional Study (NIS) Protocol

Document Number:	NA
BI Study Number:	1199-0523
BI Investigational Product(s):	Not applicable
Title:	Incidence probability of progression to progressive fibrosing interstitial lung diseases and status of management and treatments in patients with fibrosing interstitial lung diseases other than idiopathic pulmonary fibrosis in Japan
Brief lay title:	Study of progression to PF-ILD incidence/management and treatment
Protocol version identifier:	1.4
Date of last version of protocol:	29 Nov. 2023
PASS:	Not applicable
EU PAS register number:	Not applicable
Active substance:	Not applicable
Medicinal product:	Not applicable
Product reference:	Not applicable
Procedure number:	Not applicable
Marketing authorisation holder(s):	[REDACTED]
Joint PASS:	Not applicable
Research question and objectives:	
PRIMARY OBJECTIVE
 
To investigate the incidence probability of progression to PF-ILDs in patients with fibrosing ILD other than IPF in real-world setting in Japan
 
SECONDARY OBJECTIVE
 
To investigate the characteristics of procedures for management and treatment in patients with fibrosing ILD other than IPF in real-world setting in Japan

Country(-ies) of study:	Japan
Author:	[REDACTED]
Co-Author:	[REDACTED]

Marketing authorisation holder(s):	
In case of PASS, add: MAH contact person:	Not applicable
In case of PASS, add:	Not applicable
In case of PASS, add:	Not applicable
Date:	29 Nov. 2023
Page 1 of 41	
Proprietary confidential information © 2024 Boehringer Ingelheim Group of companies. All rights reserved. This document may not - in full or in part - be passed on, reproduced, published or otherwise used without prior written permission	

2. LIST OF ABBREVIATIONS

COPD	Chronic Obstructive Pulmonary Disease
CTD-ILD	Connective Tissue Disease-Interstitial Lung Disease
DPC	Diagnosis Procedure Combination
HP	Hypersensitivity Pneumonitis
HRCT/CT	High-Resolution Computed Tomography/Computed Tomography
ILD	Interstitial Lung Disease
IHD	Instant Health Data
IIPs	Idiopathic Interstitial Pneumonias
iNSIP	Idiopathic Nonspecific Interstitial Pneumonia
IPF	Idiopathic Pulmonary Fibrosis
KL-6	Krebs von den Lungen-6
MCTD	Mixed Connective Tissue disease
MDV	Medical Data Vision
PF-ILD	Progressive Fibrosing Interstitial Lung Disease
PM/DM-ILD	Polymyositis/Dermatomyositis-Interstitial Lung Disease
RA-ILD	Rheumatoid Arthritis-Interstitial Lung Disease
SAS	Statistical Analysis System
SLE-ILD	Systemic Lupus Erythematosus-Interstitial Lung Disease
SP-D	Surfactant Protein D
SSc-ILD	Systemic Sclerosis-Interstitial Lung Disease

4. ABSTRACT

Name of company: Boehringer Ingelheim Co., Ltd.			
Name of finished medicinal product: Not applicable			
Name of active ingredient:			
Protocol date: DD Month YYYY	Study number:	Version/Revision: 1.4	Version/Revision date: 29 Nov. 2023
Title of study:	Incidence probability of progression to progressive fibrosing interstitial lung diseases and status of management and treatments in patients with fibrosing interstitial lung diseases other than idiopathic pulmonary fibrosis in Japan		
Rationale and background:	
While idiopathic pulmonary fibrosis (IPF) is the best-known progressive fibrosing interstitial lung disease (PF-ILD), there is a group of patients with different underlying clinical interstitial lung disease (ILD) diagnoses other than IPF who develop a progressive fibrosing phenotype during the course of their disease.
 
There is minimal literature available to estimate the proportion of patients who develop PF-ILDs in patients with fibrosing ILD other than IPF and, the current management and treatment for these diseases are not well-known in Japan.
 
These information are keys to gaining a better understanding of the size of this population with high unmet need and for physicians, patients and other stakeholders to optimize allocation of resources, diagnostic assessment and management of this patient population.
		
Research question and objectives:	
PRIMARY OBJECTIVE To investigate the incidence probability of progression to PF-ILDs in patients with fibrosing ILD other than IPF in real-world setting in Japan
 
SECONDARY OBJECTIVE To investigate the characteristics of procedures for management and treatment in patients with fibrosing ILD other than IPF in real-world setting in Japan
		
Study design:	
This is a retrospective cohort study using the database from Medical Data Vision (MDV).
 
Data from 01-Jan-2012 to 28-May-2020 will be used. It will be considered that each patient is observable from his/her first encounter to his/her last encounter in the database. The patients with fibrosing ILD will be identified in the period from 01-Jan-2013 to 6 months before 28-May-2020. Each patient who meets all the inclusion criteria and none of the exclusion criteria will be followed up from the day after the index date until the end of study period (i.e., 28-May-2020), the last encounter in the MDV database, in-hospital death, whichever occurs first.
		

Population:	
Patients who meet all of the inclusion criteria and do not meet any of the exclusion criteria will be included in the study population.
 
Inclusion Criteria:
 
 1) Patients diagnosed with at least two fibrosing ILD codes on different dates in the patient identification period from 01-Jan-2013 to 6 months before 28-May-2020 2) Patients aged 18 years and older on the index date 3) Patients for whom data for the 12 months prior to the index date can be extracted as baseline data 
Exclusion Criteria:
 
 1) Patients grouped into the underlying disease of IPF 2) Patients who have met PF-ILD progression criteria during the baseline period 
Note: only diagnosis records without 'suspect flag' are to be considered for evaluating diagnosis related in/excl criteria"

Variables:	
The following information will be extracted from MDV database in this study; sex, age, comorbidity and medical history of interest, Underlying disease (pre-specified ILD), clinical examination, treatment and management of interest

Data sources:	
The MDV database consists of anonymized administrative claims and Diagnosis Procedure Combination (DPC) data for inpatient and outpatient settings from acute hospitals (mainly considered as advanced treatment hospitals). The database includes >35 million patients from >400 hospitals. Patients in Japan have free access to health care facilities and data from the other hospitals not included in the database are unavailable.

Study size:	
The planned sample size is not based on the formal statistical hypothesis testing and statistical precision. Because the MDV database consists of >35 million patients, it is expected that the sufficient number of non-IPF fibrosing ILD patients will be included in the study.

Data analysis:	
Primary outcome Incidence probability of progression to PF-ILDs at 6, 12, 18, and 24 months after the index date. Cumulative incidence probability will be estimated by using Kaplan-Meier method.
 
Secondary outcomes Management and treatment during follow-up period Frequency of patients with management and treatment of interest during follow-up period will be analyzed descriptively.

Milestones:	
 - Final protocol: 28 Mar 2023 - IRB approval: Prior to study start - Start of data analysis: After the IRB approval - Final results: Q2 2023 - Final study report: Q3 2023 - Publications: Q3, 2023

5. AMENDMENTS AND UPDATES

Number	Date	Section of study protocol	Amendment or update	Reason
1	28 March 2023	9.2.2.1 Exclusion Criteria	2)Patients who have met PF-ILD progression criteria during the baseline period and 3) delete	To further clarify and simplify the exclusion criteria
2	21 Sep. 2023	ANNEX 2 and 3	Add Generic names and correct ATC codes	To correct the drug codes
3	21 Sep. 2023	ANNEX 2 and 3	*transdermal patch, sublingual agent, Transmucosal agent, suppository are excluded	To reflect the updated definition of opioid use
4	10 Nov. 2023	ANNEX 2 and 3	K514-4 K514-6	To correct codes for lung transplant
5	29 Nov. 2023	ANNEX 2 and 3	N02A0	To correct the drug code for opioid

6. MILESTONES

Milestone	Planned Date
IRB/IEC approval	Prior to study start
Start of Data Analysis	After the IRB approval
Interim Report	NA
Final report of study results:	Q3 2023

7. RATIONALE AND BACKGROUND

The term interstitial lung disease (ILD) encompasses a large group of over 200 pulmonary disorders. While idiopathic pulmonary fibrosis (IPF) is the best-known progressive fibrosing ILD (PF-ILD), there is a group of patients with different underlying clinical ILD diagnoses other than IPF who develop a progressive fibrosing phenotype during the course of their disease (e.g., idiopathic interstitial pneumonias [IIPs] such as idiopathic nonspecific interstitial pneumonia [iNSIP] and unclassifiable IIP; hypersensitivity pneumonitis [HP]; autoimmune interstitial lung disease [connective tissue disease-ILDs (CTD-ILD) such as rheumatoid arthritis-ILD (RA-ILD), systemic sclerosis-ILD (SSc-ILD) and anti-synthetase syndrome]; Sarcoidosis; Pneumoconiosis/exposure related ILD) [P17-10582, P18-04729, P19-01738, R19-0854]. These patients demonstrate a number of similarities to patients with IPF, with their disease being defined by the presence of progressive pulmonary fibrosis, worsening respiratory symptoms, declining lung function despite immunomodulatory therapies and, ultimately, early mortality.

Although there had been no indicated therapies for patients with chronic fibrosing ILDs with a progressive phenotype (other than IPF), Nintedanib has just been approved for SSc-ILD in the end of Dec. 2019 based on the results of the SENSCIS trial (NCT02597933) [P19-04387] and for PF-ILDs in the end of May 2020 in Japan based on the results of the INBUILD trial (NCT02999178) [P19-08802, P20-02333].

There is minimal literature available to estimate the proportion of patients who develop PF-ILDs in patients with fibrosing ILD other than IPF in Japan. In addition, the current management and treatment for these diseases are not well-known. These information are keys to gaining a better understanding of the size of this population with high unmet need and for physicians, patients and other stakeholders to optimize allocation of resources, diagnostic assessment and management of this patient population.

Therefore, this study will use the database from Medical Data Vision (MDV) to investigate the incidence probability of progression to PF-ILDs according to each co-existing underlying diseases and the characteristics of procedures for management and treatment in patients with fibrosing ILD other than IPF.

8. RESEARCH QUESTION AND OBJECTIVES

8.1 PRIMARY OBJECTIVE

To investigate the incidence probability of progression to PF-ILDs in patients with fibrosing ILD other than IPF in real-world setting in Japan

8.2 SECONDARY OBJECTIVE

To investigate the characteristics of procedures for management and treatment in patients with fibrosing ILD other than IPF in real-world setting in Japan

[figure not shown]
9. RESEARCH METHODS

9.1 STUDY DESIGN

This is a retrospective cohort study using the database from MDV.

Data from 01-Jan-2012 to 28-May-2020 will be used. It will be considered that each patient is observable from his/her first encounter to his/her last encounter in the database. The patients with fibrosing ILD will be identified in the period from 01-Jan-2013 to 6 months before 28-May-2020. Each patient who meets all the inclusion criteria and none of the exclusion criteria will be followed up from the day after the index date* until the end of study period (i.e. 28-May-2020), the last encounter in the MDV database, in-hospital death, whichever occurs first.

*The index date will be the date of the second diagnosis of fibrosing ILD. Please refer to the Section 9.2.2.1 for the detailed codes of fibrosing ILD.

*The index date will depend on the time the patient fulfils the eligibility criteria

Figure 1 . Schematic of the Study Design

9.2 SETTING

9.2.1 Study sites

There are no study sites for this study because it is a database study.

9.2.2 Study population

9.2.2.1 Eligibility criteria

Patients who meet all of the inclusion criteria and do not meet any of the exclusion criteria will be included in the study population.

Inclusion Criteria:

- 1) Patients diagnosed with at least two fibrosing ILD codes^{*1} on different dates in the patient identification period from 01-Jan-2013 to 6 months before 28-May-2020
- 2) Patients aged 18 years and older on the index date
- 3) Patients for whom data for the 12 months prior to the index date can be extracted as baseline data

*1 International Statistical Classification of Diseases and Related Health Problems (ICD-10) code or disease code: J84.1, J84.9, 8844510, 8848382, 8844341, 8848278, 8836513, 8848267, 8848302, 8839362, 8848283, 8837013, 8834158, 8848245, 8840951, 8847737

Exclusion Criteria:

- 1) Patients grouped into the underlying disease of IPF^{*1}
- 2) Patients who have met PF-ILD progression criteria during the baseline period

*1 Please refer to the ANNEX 5 for algorithm to define underlying diseases

Note: only diagnosis records without 'suspect flag' are to be considered for evaluating diagnosis related in/excl criteria"

9.3 VARIABLES

9.3.1 Outcomes

9.3.1.1 Primary outcome

Incidence probability of progression to PF-ILDs at 6, 12, 18, and 24 months after the index date*

Progression to PF-ILD as event in this study is defined in Table 1 as well as Annex 2. Event date will be the date when the one of criteria of the progression to PF-ILD is met.

*The index date will be the date of the second diagnosis of fibrosing ILD. Please refer to the Section 9.2.2.1 for the detailed codes of fibrosing ILD.

Table 1. Interstitial lung disease progression proxies

Proxy
- ≥ 3 pulmonary function tests on different dates of service within 365 days - The date of the 3 rd pulmonary function test will be the date of progression
- ≥ 3 HRCT/CT on different dates of service within 365 days - The date of the 3 rd HRCT/CT will be the date of progression
≥ 1 claim for oxygen therapy (HOT) during follow-up period
≥ 1 respiratory hospitalization during follow-up period
≥ 1 claim for palliative care during follow-up period
≥ 1 lung transplant during follow-up period
≥ 1 new* claim for immunosuppressive drugs during follow-up period with at least two out of the three test codes** within 3 months before new claims for immunosuppressive drugs Rituximab Tacrolimus Mycophenolate Cyclosporine Cyclophosphamide Azathioprine Tocilizumab
*: Not received in the 12 months prior to the index date **: ① Pulmonary function tests, ② HRCT/CT, ③ KL-6 or SP-D
≥ 1 new* claim for oral corticosteroid with a prednisone-equivalent dose of >20 mg during follow-up period and with at least two out of the three test codes* within 3 months before new claims for oral corticosteroid *: Not received in the 12 months prior to the index date **: ① Pulmonary function tests, ② HRCT/CT, ③ KL-6 or SP-D
≥ 1 claim for Nintedanib* during follow-up period *: Patients meeting this criterion will be counted only if patients with fibrosing ILDs meet this criterion on or after 29-May-2020, because nintedanib was approved for PF-ILD on 29-May-2020. Even if patients with fibrosing ILDs meet this criterion on or before 28-May-2020, they will not be counted.

HRCT; high-resolution computed tomography, CT; computed tomography, KL-6; krebs von den lungen-6, SP-D; surfactant protein D

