9.7.2.2 Primary outcome

- Incidence probability of progression to PF-ILDs at 6, 12, 18, and 24 months after the index date

Cumulative incidence probability of progression to PF-ILD at 6, 12, 18 and 24 months after the index date will be estimated by using Kaplan-Meier method. Greenwood's variance estimate will be used for calculating 95% confidence interval. Kaplan-Meier curve will also be displayed.

Of the patients with progression to PF-ILD, frequency of patients meeting each criteria of progression to PF-ILD will be analysed descriptively.

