ANNEX 2. INTERSTITIAL LUNG DISEASE PROGRESSION PROXIES

Proxy	billing code / generic names / EphMRA ATC code
≥ 3 pulmonary function tests on different dates of service within 365 days The date of the 3 rd pulmonary function test will be the date of progression	160062610 160062710 160062810
≥ 3 HRCT/CT on different dates of service within 365 days The date of the 3 rd HRCT/CT will be the date of progression	170022290 170011710 170011810 170028610 170033410 170034910 170040210 170040410 170040610 170040810 170041010
≥ 1 claim for oxygen therapy (HOT) during follow-up period	114003710
≥ 1 respiratory hospitalization during follow-up period	A221 A379 A370 B250 B440 J00 J01.x J02.x J03.x J04.x J05.x J06.x J110 J12.x J13 J14 J15.x J160 J18.x J20x J21.x J22 J40 J41.x J42 J43.x J44.x J45.x J84.x J96.x Segment of disease based on DPC is “01: Disease name which input the most medical resources”, “11: Main disease name”, or “21: Disease name behind hospitalization”
≥ 1 claim for palliative care during follow-up period	Oxygen inhalation: 140005610 Opioid use:

	N02A0 [Excluding methadone, buprenorphine, naloxonecombinations (Suboxone)] * *transdermal patch, sublingual agent, Transmucosal agent, suppository are excluded
≥ 1 lung transplant during follow-up period	K514-4 K514-6
≥ 1 new* claim for immunosuppressive drugs during follow-up period with at least two out of the three test codes** within 3 months before new claims for immunosuppressive drugs Rituximab Tacrolimus Mycophenolate Cyclosporine Cyclophosphamide Azathioprine Tocilizumab	Rituximab/ L01G1 Tacrolimus/ L04X0 Mycophenolate/ L04X0 Cyclosporine or (Ciclosporin, Cyclosporin) / L04X0 Cyclophosphamide/ L01A0 Azathioprine/ L04X0 Tocilizumab/ M01C0 & L04C0 (Generic names/ MphMRA ATC codes which each drug is under)
≥ 1 new* claim for oral corticosteroid with a prednisone-equivalent dose of >20 mg during follow-up period and with at least two out of the three test codes* within 3 months before new claims for oral corticosteroid *: Not received in the 12 months prior to the index date **: ① Pulmonary function tests, ② HRCT/CT, ③ KL-6 or SP-D	H02A2 excluding Florinef

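### The PFT and CT progression proxies require no rise over the patient's own baseline testing, so unchanged monitoring at roughly 6-month intervals can pass exclusion 2 and later count as progression to PF-ILD

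*Combined protocol and SAP*

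**What the plan says.** Section 9.3.1.1, Table 1, repeated in Annex 2, lists the progression proxies. Two are pure test counts: "≥ 3 pulmonary function tests on different dates of service within 365 days" and "≥ 3 HRCT/CT on different dates of service within 365 days". For the first, "The date of the 3 rd pulmonary function test will be the date of progression"; the CT row is dated in the same way. One proxy is enough: "Event date will be the date when the one of criteria of the progression to PF-ILD is met".

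Section 9.2.2.1 excludes "Patients who have met PF-ILD progression criteria during the baseline period". Inclusion 3 sets the baseline: "Patients for whom data for the 12 months prior to the index date can be extracted as baseline data". On these two rows, patients with 0, 1 or 2 dates in baseline therefore enter. Under section 9.1 patients are "followed up from the day after the index date", and section 9.7.2.2 states: "Cumulative incidence probability of progression to PF-ILD at 6, 12, 18 and 24 months after the index date will be estimated by using Kaplan-Meier method".

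The other rows are built differently. The immunosuppressant and corticosteroid rows require a drug not received in the 12 months before index, plus two of three test types shortly before it. The remaining rows are expressly limited to follow-up. The PFT and CT rows carry neither a comparison with baseline nor that limit.

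**The concern.** The entry cut-off and the event threshold are the same number, and nothing in between asks whether testing increased. The two looks are also unequal. Entry checks one fixed 12-month window, whereas the event can be met in any 365-day window during follow-up. A patient with two tests a year before and after index can therefore fall just under the line at entry and cross it later.

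Section 9.9 says that the database has no PFT results, so within these rows nothing separates scheduled surveillance from testing prompted by deterioration. At stake is how the primary Kaplan–Meier estimate is read: some unknown part of it could be monitoring frequency rather than progression.

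**Working it through.** The plan states no expected incidence, event count or testing rate, so there is no figure of its own to reproduce.

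**Inputs from the documents.** Event: third test date, with third minus first at most 365 days (Table 1). Entry: fewer than 3 dates in the 12 months before index (exclusion 2, inclusion 3), taken as days −365 to 0. Follow-up starts on day 1 (section 9.1). Time points are 6, 12, 18 and 24 months (section 9.7.2.2).

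**Assumptions.** One test type; a testing rate that never changes; index date random relative to testing; no censoring; other proxies ignored; all three dates in follow-up unless stated.

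**Exact schedules.** Three tests at a fixed gap T span 2T, so the event needs 2T ≤ 365, that is T ≤ 182.5 days.
- T = 182: span 364 days, so the rule is met. A 365-day baseline window holds three such dates in only 1 of 182 alignments. About 99% pass entry, and 100% are counted by 18 months.
- T = 183: span 366 days, so the rule is never met (0%).

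**Variable schedules (simulated).**

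| Assumed testing, unchanged over time | Pass entry | Counted by 24 months |
|---|---|---|
| Mean gap 182 d, SD 14 | 95% | 70% |
| Mean gap 182 d, SD 30 | 90% | 66–68% |
| Mean gap 190 d, SD 14 | 98% | 34–35% |
| Mean gap 196 d, SD 14 | over 99% | 14% |
| Mean gap 210 d, SD 14 | 100% | about 0.6% |
| Mean gap 210 d, SD 30 | 99% | 15% |
| Yearly, SD 30 | 100% | 0% |
| Random, 1.0 per year | 92% | 22% |
| Random, 1.5 per year | 80% | 44% |
| Random, 2.0 per year | 68% | 65% |

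Check on the last entry figure: for a Poisson count with mean 2, P(≤ 2) = e⁻²(1 + 2 + 2) = 0.677.

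For 182 days with SD 14, the path over 6, 12, 18 and 24 months is about 0%, 4–5%, 53% and 70%.

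**If the window may reach into baseline.** Table 1 does not rule this out for these rows. The same schedule then gives about 51%, 68%, 80% and 88%, so about half are events by 6 months.

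**If a test falls on the index date.** At an exact 182-day gap the dates 0, −182 and −364 all lie in baseline, and nobody passes. With SD 14, 47–49% pass.

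**Effect of a minimum increase.** Require max(3, baseline count + 2) dates within 365 days. The 24-month probability then falls from 69% to 3% (182 days, SD 14) and from 68% to 7% (SD 30). Under random testing it falls only from 44% to 37% at 1.5 per year and from 64% to 53% at 2 per year. Requiring one more date than baseline changes nothing: for a patient entering with two tests, that is already the present rule.

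**The case against.** The plan is open about its weakness. Section 9.9 says that no validated algorithm exists, that the estimate might be biased, and that a different-algorithm sensitivity analysis is planned. Section 9.7.2.2 tabulates how many progressors met each proxy, so the PFT and CT share will be visible. Section 9.7.4 allows modified criteria after that table has been seen.

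This stands in part, but it does not close the gap. The only direction of bias named in section 9.9 is underestimation, from care outside the database hospitals; the mechanism here works the other way. The proxy table shows which row was met, not whether testing rose. Table 2 summarises baseline tests over 6 months, so it does not show the 12-month count. Section 9.7.4 leaves the modified-criteria analysis optional and undefined, and the two analyses it does define change only the data cut-off and the index date.

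The objections on size carry more weight:
- A reader might infer that every half-yearly patient is inevitably counted. That holds only for exact gaps of at most 182 days and fails at 183.
- The index date is a recorded diagnosis date and may coincide with a test, which makes entry much stricter.
- The figures are for a single row. Patients who reach oxygen therapy, hospitalisation or another proxy by the same time point are counted anyway.
- A reader might also infer that differences between underlying diseases are monitoring artefacts. No testing frequency by disease is given and the analysis is descriptive, so this is only a possibility.
- Putting an increase rule into the primary definition is a debatable trade: the margin of two has no source in the documents, and it helps little when testing is irregular.

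**Conclusion.** The structural point holds on the text: entry and event share one absolute cut-off, and no increase over the patient's own baseline is required. A stable patient tested at roughly 6-month intervals can therefore be counted as progressing. Under the assumptions listed, the no-change 24-month probability runs from 0% (yearly testing, or an exact 183-day gap) to about 66–70% (mean gap 182 days, SD 14–30), and it drops quickly as the mean gap lengthens beyond 182 days.

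The documents do not support reading any of these figures as the bias in this cohort's estimate. They give no testing rates, and neither censoring nor the other proxies were modelled. The bias in the composite is unknown, and the plan as written fixes no analysis that would reveal it. This should be corrected, but it is no reason to replace the primary definition.

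**What to change.** Keep Table 1 as the primary definition. In section 9.7.4, replace the optional modified-criteria analysis with three pre-specified analyses, each reported at 6, 12, 18 and 24 months:

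1. Kaplan–Meier with the PFT and CT rows requiring at least 3 dates within 365 days and at least 2 more than the patient's own 12-month baseline count of that test.
2. Kaplan–Meier without the PFT and CT rows, because the increase rule does little under irregular testing.
3. The primary estimate by 12-month baseline count (0, 1, 2) of PFT dates and, separately, of CT dates.

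In Table 1 and Annex 2, state whether all three PFT or CT dates must fall in follow-up. In section 9.9, add that routine surveillance may inflate the estimate.

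The cost is a few more tables from data already extracted. The minimum-increase version will miss or delay some true intensification: a patient with two baseline tests needs four within a year to count through that row. It therefore belongs beside the primary estimate and should not replace it.

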9.3.2 Covariates

The following information will be extracted from MDV in this study.

Table 2. Definition of variables

Variable	Data extraction period	Details
Sex	Index date	Male/Female
Age	Index date	Age at Index date
Comorbidity and medical history	12 months before the index date (included)	
 - Coronary heart disease - Gastro-esophageal reflux disease - Obstructive sleep apnoea syndrome - Chronic obstructive pulmonary disease (COPD) - Lung cancer - Pulmonary hypertension 
See Annex 4 for code to define each comorbidity and medical history

Underlying disease (Pre-specified ILD)	12 months before the index date (included)	
 - Underlying Autoimmune Disease (Autoimmune ILD, Non-autoimmune ILD, Multiple, Unknown) - ILD Category (Hypersensitive pneumonitis, Exposure-related ILD, idiopathic nonspecific interstitial pneumonia (iNSIP), Unclassifiable idiopathic interstitial pneumonias (IIP), Sarcoidosis, RA-ILD, SSc-ILD, mixed connective tissue disease-ILD (MCTD-ILD), Other autoimmune ILD, Other ILD, Multiple, Unknown) - Pre-Specified ILD Clinical Diagnosis (Hypersensitive pneumonitis, Exposure-related ILD, iNSIP, Unclassifiable IIP, Sarcoidosis, RA-ILD, SSc-ILD, MCTD-ILD, Systemic Lupus Erythematosus-ILD (SLE-ILD), Polymyositis/Dermatomyositis-ILD (PM/DM-ILD), Sjogren ILD, Other autoimmune ILD, Other ILD, Multiple, Unknown) 
See Annex 5 for algorithm to define underlying diseases

Treatment	6 months before the index date (included) Follow-up period	
 - Rituximab - Tacrolimus - Mycophenolate - Cyclosporine - Cyclophosphamide - Azathioprine - Oral Corticosteroid - Tocilizumab - Nintedanib 
See Annex 3 for code to define each treatment
 
As for corticosteroid and immunosuppressive drugs during follow-up period, the same condition used for criteria of progression to PF-ILD will be applied.

Management	Follow-up period	
 - Oxygen therapy (HOT) - Lung transplant - Palliative care (oxygen inhalation, opioid use) 
See Annex 3 for code to define each management

Clinical examination	6 months before the index date (included)	
 - Pulmonary function test - HRCT/CT - KL-6 - SP-D 
See Annex 3 for code to define each clinical examination

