9.7.2 Statistical analysis

9.7.2.1 Patient background characteristics and treatment

- Patient demographics (sex, age at the index date)
- Comorbidity and medical history during 12 months prior to the index date (included)
- Clinical examination, management, and treatment during 6 months prior to the index date (included)
- Duration of follow-up period, which is defined as “end of follow-up period” – “start of follow-up period” + 1 day
- Underlying diseases

These will also be analysed in patients with progression to PF-ILD and those without progression to PF-ILD respectively.

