9.7.2.3 Secondary outcomes

- Management and treatment during follow-up period

Frequency of patients with management and treatment during follow-up period will be analyzed.

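### A 'new' immunosuppressant or oral-corticosteroid claim is judged against the baseline period itself, so baseline starts cannot trigger exclusion criterion 2, and follow-up use of 8 of 9 listed drugs is counted only in patients who met a progression proxy

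*Combined protocol and SAP*

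**What the plan says.** Section 9.3.1.1, Table 1, lists nine progression proxies. Two are drug starts, one for immunosuppressants and one for oral corticosteroid. Both need a *new* claim in follow-up, footnoted as "Not received in the 12 months prior to the index date". Annex 2 repeats the rule, printing the footnote in the corticosteroid row. Both rows also need tests; for immunosuppressants the claim must come "with at least two out of the three test codes within 3 months before new claims for immunosuppressive drugs". The corticosteroid row adds a dose condition. The event is dated when a criterion is met, and section 9.1 starts follow-up on the day after index.

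In section 9.2.2.1, inclusion criterion 3 takes the 12 months before index as baseline data. Exclusion criterion 2 removes "Patients who have met PF-ILD progression criteria during the baseline period". No separate baseline version of the proxies is given.

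Section 9.3.2, Table 2, lists nine treatments, extracted over the 6 months up to and including index and again over follow-up. For follow-up it adds: "As for corticosteroid and immunosuppressive drugs during follow-up period, the same condition used for criteria of progression to PF-ILD will be applied". Section 9.7.2.3 then plans: "Frequency of patients with management and treatment during follow-up period will be analyzed".

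**The concern.** One rule serves three purposes: removing patients who have already progressed, dating progression afterwards, and describing treatment. It is built for the second only.

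For the first purpose, the look-back and the baseline period are the same window, so the rule cancels itself. The primary analysis is meant to start from patients who have not yet progressed. Those whose only sign of baseline progression is a drug start after work-up remain in it.

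For the third, the secondary objective is to describe management and treatment in patients with fibrosing ILD. A count restricted to progression-type starts answers a narrower question, and a reader of the table would take it for treatment use.

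**Working it through.** The documents give no rate or count for this point, so there is no stated figure to reproduce. The check applies the written rule to the calendar and to constructed claim histories. Day 0 is the index date, the look-back and baseline are days −365 to −1, and follow-up starts on day 1. Assumed for illustration: refills every 28 days and 3 months = 91 days.

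**1. Exclusion criterion 2.** A claim on any day from −365 to −1 is itself receipt in the look-back. Baseline days on which a claim can be *new*: 365 − 365 = 0. If the index day counts as baseline but lies outside the look-back: 366 − 365 = 1. This does not depend on whether *not received* is per drug or per class. For corticosteroid it does not depend on whether any dose or only the stated dose condition counts, because a qualifying baseline claim is receipt under every reading.

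**2. Does moving the window help?** Oxygen therapy, respiratory hospitalization, palliative care and lung transplant are also tied to follow-up. Reading baseline for follow-up makes those four usable for criterion 2. It does not help the two drug rows, because the look-back stays fixed at index.

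**3. Example.** CT and KL-6 on day −70, first tacrolimus claim on day −60, no other proxy in baseline. As written, this patient is not excluded and can have no later event through tacrolimus. An event through another proxy remains possible.

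**4. Follow-up treatment.** Nine drugs are listed and all but nintedanib carry the progression condition: 9 − 1 = 8. Everyone counted for those 8 has by definition met a progression proxy. Starters without the tests are not counted, nor are continuing users of an immunosuppressant. For corticosteroid, continuing users are not counted if *not received* means any dose. If it means only claims meeting the dose condition, some would count.

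**5. Does the baseline table fill the gap?** Only in part. Taking 6 months as 183 days, it misses days −365 to −184: 365 − 184 + 1 = 182 of the 365 look-back days. A patient whose pre-index claims all fall there, and who takes the drug in follow-up, appears in neither table.

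**6. What the text leaves open.**

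- *First fill or any fill.* Drug first filled on day 60 without tests; CT and KL-6 on day 300. Refills fall on day 60 + 28n, so the next after the tests is 60 + 28 × 9 = day 312, which is 12 days later and inside 91. If every claim of a drug absent from the look-back is *new*, the event is on day 312. If only the first fill is *new*, there is none.
- *Index day.* Drug first filled on day 0; tests on day −14. If day 0 is outside the look-back and the patient is not excluded at baseline, the day-28 refill is an event (28 + 14 = 42 days after the tests). If day 0 is inside, there is none. Table 2 marks its look-backs as including the index date; the *new* footnote does not.
- *Drug or class.* Tacrolimus from day −60, mycophenolate first filled on day 120, tests on day 110. Event on day 120 if judged per drug, none if per class.

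**7. Direction.** The patients kept through step 1 cannot have an event through that drug, which pulls the estimate down. They may have more or fewer events through other proxies than the rest of the cohort. The documents settle neither their number nor the net sign.

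**The case against.** The strongest reply is that a programmer would read *new* sensibly and adapt it for baseline. For refills this has force: a first-claim reading is natural, so the text is ambiguous there and not fixed in error. For exclusion criterion 2 it does not rescue the plan, because the obvious adaptation fails (step 2) and any other means writing a rule that the protocol does not contain.

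Second, the plan has safeguards. Section 9.9 says that a different algorithm is planned to test robustness, but section 9.7.4 says only that modified criteria might be used, without content. Its two specified analyses move the data cut-off or the index date and leave the look-back tied to index. Section 9.7.2.2 plans: "Of the patients with progression to PF-ILD, frequency of patients meeting each criteria of progression to PF-ILD will be analysed descriptively". That caps how many patients the refill question can affect. It cannot show who was wrongly kept, nor separate starts from refills.

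Third, Table 2 declares its condition openly and tabulates baseline use. True, but declaring the restriction does not make the count answer the secondary objective.

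Fourth, a first-claim-only rule has a cost of its own. Suppose corticosteroid is first claimed on day 30 without meeting the dose condition, and a day-300 claim meets it after CT and KL-6. That can be an event as worded, but never under a first-claim-only rule. This stands, and it is why the fix asks for the choice to be stated and tested, not for one reading to be imposed.

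**Conclusion.** Two defects stand on the text as written. Exclusion criterion 2 cannot operate through 2 of the 9 proxies (0 of 365 baseline days, or 1 of 366 under one index-day reading). The follow-up frequencies for 8 of the 9 listed drugs describe patients who met a progression proxy, not treatment use. The first-claim, drug-or-class and index-day questions are ambiguities that can change event dates.

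A reader might infer more than this.

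- *That criterion 2 does nothing.* It still works through other proxies, so patients who also meet one of those in baseline can be excluded.
- *That refills of a drug already claimed in the look-back become events.* They are not *new*; the refill question concerns drugs first claimed after index, or on the index day under one reading.
- *That the incidence estimate is biased by a known amount or in a known direction.* The documents give no number of such patients and no event risk for them. An earlier event through another proxy can also pre-empt a refill.
- *That nintedanib belongs to the same fault.* It has no new-use condition and cannot count in the main analysis. Refills in prior users are a separate matter for the extended-data sensitivity analyses only.

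**What to change.** 1. **Exclusion criterion 2.** Write a baseline version of the two drug proxies, anchored at the claim: no receipt of that drug in the observable data up to 12 months before it, with the existing test and dose conditions kept. Report the number excluded by this route and the primary estimate with and without them.
2. **Table 2.** Report any use of each drug in follow-up beside qualifying new use.
3. **Meaning of *new*.** State whether it is the first post-index claim or any claim, whether it is per drug or per class, whether prior corticosteroid means any dose, and on which side the index day falls. Report the primary estimate under the other claim reading as a sensitivity analysis.

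The cost is amended wording in Table 1, Table 2, Annex 2 and section 9.2.2.1, and reprogramming of data already held.

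Item 1 has a real downside. Only 12 months before index are guaranteed, so a claim on day −k has 365 − k guaranteed look-back days: 305 at k = 60, 65 at k = 300. Data start on 01-Jan-2012, so index dates in 2013 cannot have 24 months behind them. That is 365 of the 2,523 identification days from 01-Jan-2013 to 28-Nov-2019, or 14.5% of calendar time (not of patients). Section 9.4 adds that other hospitals' data are unavailable. Some maintenance users newly seen in the database may therefore be excluded as starters. How many cannot be told from the documents, which is the reason for the with-and-without report.
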